Study banners will be created by Public Health Solutions for recruitment of PLWHA with HANA conditions for the aforementioned survey. The study banners will route people to our study landing page. We conservatively estimate that at least 50% of all PLWHA in the US suffer from at least 1 HANA condition based on our review of the literature (Crothers et al., 2006; A. Justice & Falutz, 2014; A. C. Justice, 2010; A. C. Justice, 2014; A. C. Justice et al., 2004; Kendall et al., 2014; Messeri et al., 2009; So-Armah & Freiberg, 2014). Given this estimate, of the 150,000 PLWHA who use POZ.com as well as additional PLWHA with HANA conditions who use Facebook, we should easily be able to collect our study data within our study timeframe. [name] collaborated with POZ on a brief online pilot in NY, CA and GA, sending emails to a defined subset of HIV+ male members identifying as gay or bisexual (n=5,262). POZ's email system can target members by location, sexual orientation, race/ethnicity, age, and most recent log-on. Of the 5,262 emailed, 1,696 (32%) clicked through; 479 of those who clicked through consented (28%); and 464/479 completed the survey (97%). In 7 days, through direct email with POZ Personals members, we were able to collect 463 completed cases. For the proposed study, we will be using banner ads on POZ and may not have the same response rate; however, 4 months is a sufficient amount of time to recruit 1,000 participants, given our inclusion criteria.

During the initial stages of survey collection for Aim 1a we detected a significant gender disparity in our population being mostly males completing the survey. Due to this difficulty recruiting women, in an effort to increase the number of female participants we will close the enrollment for males at this time. We have modified our survey to include female reproductive system questions and created a recruitment flyer offering \$10 as an incentive for female survey takers. A new survey has been created for this purpose.

See Attachment: VIP HANA Women Qualtrics Survey.pdf

For this purpose, we will launch a paid online campaign through POZ.com as well as flyers posted around the Columbia hospital and surrounding areas as well as other social media sites to include more women and reduce gender disparity. Online female survey takers will receive a \$10 amazon gift code while on site female survey takers, recruited through posted flyers, will receive \$10 in cash.

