Data Analysis: Frequency of symptom reporting will be calculated. Our analysis will look for differences in symptom reporting and self-care strategies based on HANA condition, age and/or gender. We anticipate that there will be differences in gender but not in age (See Section C.2.1 below). Symptoms must be attributed to a HANA condition to be included as part of the final list of symptoms in our intervention. We anticipate that some self-care strategies will be the same for different conditions. In other cases, strategies will be different and the VIP-HANA system will deliver a self-care strategy tailored to symptom reporting, HANA condition(s) and gender, if applicable. Content analysis will be used to analyze the self-care strategies and attribution data for inductive development of the category schemes. Initial codes or categories of self-care strategies will be identified inductively from the data. To reduce the number of categories, initial codes will be consolidated on the basis of theoretical similarities and clinical significance after consultation with our study team. Drs. [name], [name], [name] and the research assistant will collaborate on this analysis. We will also categorize the self-care strategies by information source reported by the survey respondent. Strategies which are potentially harmful or illegal (e.g., substance use) will not be included in VIP-HANA. We will have precautions in place to advise patients who appear to be at-risk for negative outcomes (e.g., report of severe depression) to contact their healthcare provider, call 911 or go directly to the emergency room.

Study Team and Experts will finalize the symptom list and self-care strategies: In year 2, we will conduct a meeting with the study team and the EAB to finalize the symptom list and the self-care strategies to be included in the VIP-HANA system. Once this has been finalized, technical refinement of our existing web app will take place at CBITs (see facilities and resources). We have partnered with CBITs since they use Purple, an extensible, modular, and re-purposable system created for the development of Web-based and mobile-based applications for health behavior change (Schueller, Begale, Penedo, & Mohr, 2014). [name] (PI: CBITs) is the Site PI for this project. Figure 4 illustrates a sample screen created by CBITs of self-care strategies for depressive symptoms. In response to the reviewer's request, a letter of support

from the technical team is included.

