- 6) Report at least 8 symptoms. Possible symptoms include: fatigue or loss of energy, sadness/depression, muscle aches/pains, difficulty falling asleep, difficulty staying asleep, nervousness/anxiety, difficulty remembering, pain/numbness/tingling in hands or feet, trouble concentrating, decreased sex drive, diarrhea/loose bowel movement, difficulty achieving or maintaining an erection (males only), shortness of breath, constipation/bloating/gas, thirst/dry mouth, difficulty with balance/clumsiness/dropping things frequently, unplanned weight changes, dizziness/lightheadedness, heartburn/acid reflux, dry eyes, changes in appetite, ringing in ears or intolerance to noise, cough, nausea/vomiting, fevers/chills, sweats, difficulty with urination, speech difficulties, pain or discomfort during sex
- 7) Taking antiretroviral therapy (ART).

While we anticipate that HANA conditions will be more prevalent in persons over age 50, we have not limited our inclusion criteria to this age range. We are collecting participants' age and will include that as a covariate in our final analysis. If our results in Aim 1 demonstrate a gross difference in symptom reporting and self-care strategies related to age of participants then the study team and external advisory board will meet and consider revising the inclusion criterion of age for the RCT.

Exclusion criteria include: pregnancy, unable to understand the consent procedure, and self-reporting no symptoms within the previous week or concurrent participation in a mobile app study for PLWHA including text messaging studies and any clinical problems that would not allow someone to use a cell phone or fulfill study procedures including meeting the criteria for dementia. Prior to participating in any study procedure, all potential participants must voluntarily provide informed consent.

Sample: We will recruit 5 PLWHA with HANA conditions to participate in a pilot and 100 PLWHA with HANA conditions to participate in a 6-month trial (see recruitment plan). They will be told the purpose of the study is to improve the quality of life of PLWHA. Sample size and statistical power calculations are based on the hypothesis test of improvement of symptom status after the use of VIP-HANA and on the comparison of the effect of VIP-HANA to the control group.

The intervention group will have access to VIP-HANA, a web app that provides self-care strategies tailored to symptom reporting, HANA condition(s) and gender. Both the control and

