Randomization: This will be a single-blinded study, with subjects blinded to study group assignment. Patients will be randomized (1:1) to VIP-HANA or an attention control group. Both groups will receive secure messaging reminders via their smartphone and will also be asked to report their symptoms on their smartphone via a web app every week. Participants in the VIP-HANA (intervention) group will also receive symptom strategies tailored to symptom reporting, HANA condition(s) and gender. Details of the differences between the intervention and control group can be found above in Table 5 (see Section D.1.b).

Data collection: We will have two levels of data collection.

- 1) Participants will report on their symptom frequency and intensity every week on the VIP-HANA app. Participants in both groups will receive reminder messages to report symptoms every week via the revised Sign and Symptom Check-List for HIV delivered via email. If a participant has not completed the checklist in more than 3 weeks, he/she will receive a reminder email or phone call. Intervention arm participants will complete the revised Sign and Symptom Check-List for HIV every week and receive tailored self-care strategies based on their symptom reporting, HANA condition, and gender. Control arm participants will complete the revised Sign and Symptom Check-List for HIV, but will NOT receive strategies.

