- 2) Participants will complete all secondary study-related questionnaires (see outcome measures below) via an electronic survey at baseline, at a 3-month follow-up visit (after 12 weeks), and at the end of the study at a 6-month follow-up visit (week 26). Participants will complete the study questionnaires at our study site. The survey will be housed on Qualtrics software which is a web-based survey program freely available to Columbia University Medical Center employees. Qualtrics provides a secure HIPAA protected environment. Participants will also complete physical measures at all 3 time points. Participants' height, weight, grip strength, and time taken to walk 15 feet will be measured. We will also abstract information from their medical records, such as CD4 counts and viral load, as indicated in the grant submission. In addition all participants will complete demographic information and other related measures including PHQ-2 (Hirshfield et al., 2008; Kroenke, Spitzer, & Williams, 2003), GAD-2 (Kroenke, Spitzer, Williams, Monahan, & Lowe, 2007), HIV stigma (Berger, Ferrans, & Lashley, 2001; Bunn, Solomon, Miller, & Forehand, 2007), health literacy (Weiss et al., 2005), eHealth literacy (Norman & Skinner, 2006), and perceived social support (Brock, Sarason, Sarason, & Pierce, 1996; Kalichman et al., 2006). In response to the reviewers' concern, all participants will complete the social desirability scale (Reynolds, 1982) which will be included in our final analytic model.

Participants will receive \$25 for completion of study questionnaires at baseline, \$35 at the 3-month follow-up visit, and \$40 at the 6-month follow-up visit for completing the assessment tools. Each week that a participant completes a session of the VIP HANA app, they will be given \$5 (26 weeks x \$5/week = \$130). If a participant does not miss more than 5 sessions, they will earn a bonus of \$20. Participants are eligible for up to \$250.

Outcome Measures. Our primary outcome measures, symptom frequency and symptom intensity, will be measured at baseline and every week for 26 weeks. We used the same study-

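### Gender is not named as a covariate in the RCT's primary models, although the plan expects differences by gender rather than age; adding it costs almost nothing

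*Combined protocol and SAP*

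**What the plan says.** All references are to the combined protocol and SAP.

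- **Specific Aim 2, Setting and Sample**, in the paragraph explaining why enrolment is not limited to people over 50, the plan says that it collects participants' "age and will include that as a covariate in our final analysis".
- **Specific Aim 2, Procedures, Data collection:** "all participants will complete the social desirability scale (Reynolds, 1982) which will be included in our final analytic model". The same paragraph says that all participants supply demographic information.
- **Specific Aim 2, Data Management and Analysis:** a linear mixed model for symptom intensity and a negative binomial mixed model for symptom frequency. No covariates are listed for either.
- **Specific Aim 2, Randomization:** "Patients will be randomized (1:1) to VIP-HANA or an attention control group". No stratification factor or minimization is stated. On tailoring: "Participants in the VIP-HANA (intervention) group will also receive symptom strategies tailored to symptom reporting, HANA condition(s) and gender".
- **Specific Aim 2, eligibility criterion 6:** the symptom list includes "difficulty achieving or maintaining an erection (males only").
- **Specific Aim 1a, Data Analysis**, after saying that symptom reporting and self-care strategies will be compared by HANA condition, age and/or gender: "We anticipate that there will be differences in gender but not in age".
- **Specific Aim 1a, Recruitment:** "we detected a significant gender disparity in our population being mostly males completing the survey".

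Gender does not appear anywhere as a covariate, stratification factor, interaction or subgroup for the RCT.

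**The concern.** The primary outcomes are symptom frequency and intensity. The plan's only stated expectation about which demographic variables go with symptom reporting favours gender over age, and the item list gives men one possible symptom that women cannot report. The model text nevertheless commits to age and does not mention gender.

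With 50 people per arm and no stated stratification, the arms can differ noticeably in gender by chance. If gender predicts the outcome, that difference moves the estimated arm effect in the trial actually run, and neither the design nor the two named covariates corrects it. Leaving gender unnamed also leaves room to decide on its inclusion after the data are seen.

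**Working it through.** The plan gives no figure on this point to reproduce. It states neither the RCT's expected gender mix nor the size of any gender difference in symptoms. Both are assumed below and shown as ranges.

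**Inputs from the plan:** 50 per arm, falling to 40 per arm after 20% attrition; a 10% between-arm difference in symptom frequency, which is 0.10 × 8 = 0.8 symptom on the plan's example average of 8.

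**Assumed inputs:** 20-50% women; a gap of 1-3 symptoms between men and women; SD of the symptom count 4-5.

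**1. Chance of imbalance.** Take K women among 100 people split at random into two arms of 50. The number in one arm is hypergeometric(100, K, 50). P(the arms differ by at least 10 percentage points in gender):

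| Women, K of 100 | Probability |
|---|---|
| 20 | 21% |
| 30 | 28% |
| 40 | 31% |
| 50 | 32% |

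With K even, the difference in women between arms is always even, so 10 points (5 women) in practice means 6 or more. Drawing each arm's count as an independent binomial instead gives 26-37%. At 40 per arm the figures are 40-50% (hypergeometric) and 33-43% (binomial).

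**2. Shift in the arm comparison.** Shift = gender gap × imbalance.

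- Gap 1: 1 × 0.10 = 0.1 symptom; 0.1/0.8 = 13% of the target effect.
- Gap 3: 3 × 0.10 = 0.3 symptom; 0.3/0.8 = 38%.

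Against sampling error: the standard error of a single two-arm comparison is SD × √(2/50) = 0.2 × SD, or 0.8 to 1.0 symptom. The shift is therefore between 0.1/1.0 = 0.1 and 0.3/0.8 ≈ 0.4 of one standard error.

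**3. Effect of the entry rule.** Everyone enrolled reports at least 8 symptoms, which compresses a gender gap at entry. Assume negative binomial counts, a mean of 6-10 before screening in the lower group, SD 4-5 and a cap of 29. A gap of 1-3 before screening then becomes about 0-1.8 after it, so a 10-point imbalance shifts the entry difference by about 0-0.18 symptom. Some of the gap could return during follow-up.

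**4. Precision.** Share of variance explained by gender = gap² × f(1 − f)/SD², with f the proportion of women.

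- Gap 1, f = 0.3, SD 5: 1 × 0.21/25 = 0.8%.
- Gap 3, f = 0.5, SD 4: 9 × 0.25/16 = 14%.

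**5. Error rates.** Simulation of a single normal outcome, 40 per arm, gender effect 0.5 SD:

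| Women | Type I error, unadjusted | Type I error, adjusted | Power, unadjusted | Power, adjusted |
|---|---|---|---|---|
| 30% | 4.6% | 4.8% | 79.8% | 81.0% |
| 50% | 5.3% | 5.2% | 79.7% | 80.7% |

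The power columns use an arm effect of 0.65 SD, chosen so that the unadjusted test has about 80%. Adjustment gains about 1 point.

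**The case against.** - **No closed covariate list exists.** A reader might infer that the plan lists its covariates and that the list contradicts its own expectation. The text does not support that. Age is mentioned while explaining the age criterion and social desirability in reply to a grant reviewer's concern, and the analysis section lists nothing. Gender is unnamed, not excluded. This stands.
- **The gender expectation belongs to the Aim 1a survey.** It covers self-care strategies as well as symptom reporting, so it does not establish that gender predicts the total symptom count in the RCT. This stands in part. Symptom reporting is one of the two things covered and is also the RCT's primary construct, so the expectation is relevant without being proof.
- **Age has its own rationale.** The plan expects HANA conditions to be more prevalent over age 50 and allows the age criterion to be revisited after Aim 1. This stands, and age should stay in the model.
- **Randomization already protects the comparison.** A reader might infer that omitting gender biases the result or inflates false positives. It does neither: type I error is near 5% either way, and the usual interval already allows for chance imbalance. This stands.
- **Baseline adjustment would absorb most of a stable gender gap**, as would a contrast in change. That is true, but the plan states neither baseline adjustment nor the treatment contrast.
- **Availability of gender.** One might argue that the app's tailoring makes gender known for everyone. Tailored strategies reach only the intervention arm, so availability rests on the demographics collected from all participants.

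**Conclusion.** The point holds as a free improvement. The plan commits to age and social desirability and leaves gender unnamed, although its only stated expectation favours gender and one symptom item applies only to men. It is an omission from a covariate specification that was never completed, not an internal contradiction and not a threat to validity.

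The firmest number is the 21-32% chance of a 10-point imbalance at 50 per arm, which needs only the assumption of 20-50% women. The consequences rest on an assumed gender gap and SD: a shift of 0.1-0.3 symptom at most under the ranges used, less once the 8-symptom entry rule is allowed for, and less again with baseline score in the model. The expected power gain is about 1 point at a gender effect of 0.5 SD.

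**What to change.** In Data Management and Analysis, state the covariates for both primary mixed models (symptom frequency and symptom intensity): age and social desirability as already planned, plus gender as a prespecified fixed effect. State in the same place whether baseline symptom score is included, because that determines how much gender adds.

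The cost is one line of text and about one degree of freedom. No new data are needed, provided the baseline demographic form, whose items the plan does not list, records gender; this should be confirmed.

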The power calculation for this study is not based on the feasibility study effect size as this was a pre-post study design and does not present equivalency to this study design. The purpose of the feasibility study was to show that participants are willing to use the system and that there was some meaningful change in symptom reporting after use of the VIP system (Bowen et al., 2009). The power analysis for this study is calculated to detect a clinically meaningful change in symptom frequency. For symptom frequency outcomes, 100 subjects gives more than 80.7% power to detect 13% decrease in symptom frequency (for example, from an average 8 symptoms to an average 7 symptoms) from the baseline to the end of study (i.e., 26th week). For the comparison between the control group and the VIP-HANA group, 100 subjects gives 82.4% power to yield a statistically significant result (assuming an intention-to-treat principle for the analysis) to test 10% difference in VIP-HANA over the control group (i.e., a decrease in symptom frequency). For the symptom intensity outcomes, the proposed sample yields at least 92.3% power to detect decrease in symptom intensity score of a small effect size of 0.1 from the baseline to the end of study. For the comparison of the two groups, this study will have about 87.4% power to yield a statistically significant result to test a small effect size of 0.24 difference in symptom intensity score for the VIP-HANA group over the control group.

Procedures

Recruitment Plan: We will post flyers at local clinics and community based organizations throughout New York City. Potential participants will be pre-screened for eligibility over the phone by study staff. In order to ensure that an eligible participant arrives at their visit, they will receive a confirmation email for their baseline visit which will be generated by REDCap.

Pilot: We will conduct a recruitment pilot that enrolls 5 PLWHA with at least 1 HANA condition

before the 6-month trial. This pilot will allow us to determine ease and feasibility of recruiting PLHWA that have HANA conditions, as well as examining any issues there may be in retention and adherence with regard to usage of the VIP-HANA app. Those enrolled in the pilot will follow the same procedure (randomization, data collection) as those enrolled in the 6-month trial.

Trial: We will enroll 100 PLHWA with HANA conditions in a 6 month trial with a baseline, 3 month and 6 month measurement.

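### Two of the four power figures are for uncontrolled before-after change, and the baseline-adjusted between-arm test that Aim 2 needs is not written down

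*Combined protocol and SAP*

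**What the plan says.** The Sample text under Specific Aim 2 gives two bases for the sample size: a "hypothesis test of improvement of symptom status after the use of VIP-HANA", and a second calculation "on the comparison of the effect of VIP-HANA to the control group". The power paragraph just before Procedures gives one figure of each kind for each primary outcome.

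- Frequency, before-after: "100 subjects gives more than 80.7% power to detect 13% decrease in symptom frequency", illustrated as a fall from 8 symptoms to 7 by week 26.
- Frequency, between arms: "100 subjects gives 82.4% power to yield a statistically significant result", for a 10% difference.
- Intensity, before-after: "the proposed sample yields at least 92.3% power to detect decrease in symptom intensity score of a small effect size of 0.1", again from baseline to the end of study.
- Intensity, between arms: about 87.4% for an effect size of 0.24.

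The same paragraph declines to use the feasibility study's effect size because "this was a pre-post study design and does not present equivalency to this study design".

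Hypothesis (a) and the statement of Specific Aim 2 both set VIP-HANA against control. Under Data Management and Analysis, a linear mixed model is planned for intensity and a negative binomial mixed model for frequency. No treatment contrast, time point or handling of baseline is stated. Two covariates are named. For age, Eligibility Criteria says the team "will include that as a covariate in our final analysis". Data collection adds the social desirability score. Outcome Measures says that symptoms are recorded at baseline and weekly for 26 weeks.

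**The concern.** A fall in symptoms from baseline to week 26 among people using VIP-HANA mixes the effect of the strategies with everything else that changes over six months. Table 2 and the Randomization text show that controls also report weekly and receive reminders, so self-monitoring acts in both arms. Entry requires participants to "Report at least 8 symptoms", which selects on the primary outcome, so some fall may come from regression to the mean. Only the comparison with control removes these components.

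The plan nonetheless calls the before-after change a hypothesis test and gives it the highest power in the document (92.3%). Because the analysis section does not write out the between-arm contrast, the text leaves room to report a within-arm fall as a test result. It also leaves open whether the between-arm test will use the baseline symptom value, which the trial collects and which is likely to be among the best predictors of later symptoms.

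**Working it through.** **Step 1. What each figure tests.** All four come from the power paragraph, at N=100 and two-sided alpha 0.05.

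| Outcome | Contrast | Effect | Stated power | Tests Aim 2? |
|---|---|---|---|---|
| Frequency | Baseline to week 26 | 13% fall | 80.7% | No |
| Frequency | VIP-HANA vs control | 10% difference | 82.4% | Yes |
| Intensity | Baseline to week 26 | 0.1 | 92.3% | No |
| Intensity | VIP-HANA vs control | 0.24 | 87.4% | Yes |

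**Step 2. Can the figures be reproduced?** I used a normal approximation with critical value 1.960.

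- *Between-arm intensity.* At one time point with 50 per arm, power = Φ(0.24 × √(50/2) − 1.960) = Φ(−0.760) = 22.4%. With 40 per arm it is Φ(0.24 × √(40/2) − 1.960) = Φ(−0.887) = 18.8%. To reach 87.4% with 50 per arm, the variance must shrink by the factor (0.24/(1.960 + 1.146))² × 50/2 = 0.149. If 26 weekly reports are averaged, (1 + 25ρ)/26 = 0.149 gives a within-person correlation ρ of about 0.115. With 40 per arm, ρ is about 0.084. A single endpoint adjusted for baseline would need a correlation of about 0.92 to 0.94.
- *Between-arm frequency.* I take 10% of the plan's example mean of 8, a difference of 0.8. Power of 82.4% needs an SD of 0.8/(2.891 × √(2/50)) = 1.38 with 50 per arm, or 1.24 with 40. With Poisson variance (my assumption) at one time point, power is 30.5% or 25.4%.
- *Before-after frequency.* For a fall of one symptom, 80.7% needs an SD of change of √n/2.827, which is 3.54 at n=100, 2.50 at n=50 and 2.24 at n=40.
- *Before-after intensity.* If 0.1 is in SDs of change, power at n=100 is Φ(0.1 × √100 − 1.960) = 16.9%. If it is in SDs of a single score, 92.3% at n=100 needs a standardised change of 3.386/√100 = 0.3386, so a baseline-to-end correlation of 1 − (0.1/0.3386)²/2 = 0.956. At n=40 the correlation needed is 0.983.

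The plan gives no SD, overdispersion, within-person correlation or metric for its effect sizes. None of the four figures can be confirmed from the documents. None is refuted either, because a repeated-measures calculation with favourable inputs could give them.

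**Step 3. What remains without the before-after figures.** The stated 82.4% and 87.4%, both at N=100, remain. On the plan's own numbers the sample size does not move.

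**Step 4. What baseline adjustment can gain.** For one continuous week-26 measurement with baseline-to-week-26 correlation r, the variance of the adjusted between-arm difference is 1 − r² of the unadjusted one. The documents give no r, so I assume a range:

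- r = 0.3: 1 − 0.09 = 0.91
- r = 0.5: 1 − 0.25 = 0.75
- r = 0.7: 1 − 0.49 = 0.51

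These ratios indicate scale only. They do not carry over directly to weekly mixed models or to the negative binomial model.

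**The case against.** The case against is that little turns on this. The randomised comparison appears in the aim, in the hypothesis, in the basis for the sample size and in the power paragraph. Each primary outcome has its own between-arm figure above 80%, and the analysis section plans no before-after test as confirmatory. A mixed model with baseline in the repeated outcome would also use the baseline value already. All of this stands. It limits the first half of the point to the standing of two figures, and it reduces the gain from the second half if that is the model intended. The plan does not say that it is.

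Four stronger readings are tempting, and the documents do not support them.

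- *The trial is too small.* The between-arm figures are unverified, which is not the same as wrong.
- *The before-after figures are inflated because only 50 people receive strategies.* If they were computed on 100, the noncentrality of 2.827 or 3.386 times √0.5 gives 1.999 or 2.394, so about 52% or 67% power in one arm of 50. Going on to 40 completers (√0.4) gives 43% or 57%. But the between-arm figure is also worded for 100 subjects, so the words may mean enrolment. If 80 were analysed, 43% and 57% count attrition twice. If one arm was used, nothing changes.
- *Regression to the mean explains the target fall.* The Recruitment Plan describes a phone pre-screen before a separate baseline visit. If the 8-symptom count is taken on that call, much of the regression may occur before baseline. The documents do not settle this.
- *The plan contradicts itself over pre-post evidence.* It declines to borrow an effect size from a differently designed study. That is not a rejection of estimating within-person change, though the same reasoning shows why such a change cannot stand in for the randomised comparison.

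**Conclusion.** The point holds and is minor. Two of the four power figures (80.7% and 92.3%) belong to a test that cannot support the between-arm Aim 2 hypothesis, and the Sample text should not rest the sample size on it. N=100 keeps its stated between-arm justification, subject to inputs that the plan does not report.

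The change with practical effect is in the analysis section. The between-arm contrast is not stated there, and the baseline symptom value is not among the named covariates. Adjusting for it guards against chance baseline imbalance and should give equal or better precision. The size of that gain under the planned models cannot be computed from the documents. The range of 0.91 to 0.51 applies only to a single continuous week-26 measure at assumed correlations of 0.3 to 0.7.

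**What to change.** 1. In the Sample text and the power paragraph, label within-arm change as descriptive and state its n, or delete it. Rest N=100 on the between-arm figures, and give the SD, overdispersion, within-person correlation and time point behind them so that they can be checked against the contrast in item 2.
2. Under Data Management and Analysis, name the between-arm contrast at week 26, which the sample-size text treats as the end of study, as the confirmatory test for each primary outcome. Use the post-baseline weekly reports as the outcomes. Enter baseline symptom count (frequency model) or baseline intensity (intensity model) as a covariate, alongside age and social desirability. Do not also keep baseline in the outcome vector.

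The cost is that two favourable power figures lose their standing and each model gains one covariate. Baseline symptoms are already collected, so no new data are needed, and the planned enrolment is unchanged. A participant with no post-baseline report adds nothing to such a model, so the number of these should be reported by arm.
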